12.8.4 Evaluation of organ enlargement¹¹

Complete Response (CR): Regress to normal

Partial response (PR): Spleen must have regressed by >50% in length beyond normal

Stable Disease (SD): No increase consistent with progression

Progressive Disease (PD): In the setting of splenomegaly, the splenic length must increase by 50% of the extent of its prior increase beyond baseline. If no prior splenomegaly, must increase by at least 2 cm from baseline.

New or recurrent splenomegaly

12.9 Best Response

Two objective status determinations of disease status, obtained on two consecutive determinations, separated by at least a 3 week time period, are required to determine the patient's overall best response. Two objective status determinations of CR before progression are required for best response of CR. Two determinations of PR or better before progression, but not qualifying for a CR, are required for a best response of PR. Two determinations of stable/no response or better before progression, but not qualifying as CR or PR, are required for a best response of stable/no response; if the first objective status is unknown, only one such determination is required. Patients with an objective status of progression on or before the second evaluations (the first evaluation is the first radiographic evaluation after treatment has been administered) will have a best response of progressive disease. Best response is unknown if the patient does not qualify for a best response of progressive disease and if all objective statuses after the first determination and before progression are unknown.

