This subprotocol is a component of the NCI-COG Pediatric MATCH trial APEC1621. The APEC1621SC screening protocol details the assay used for the integral genomic profiling which will determine eligibility for this subprotocol. Here we will conduct a phase 2 trial of tazemetostat in children with recurrent or refractory solid tumors (including non-Hodgkin lymphomas, histiocytoses and CNS tumors) harboring specified activating genetic alterations in EZH2 or members of the SWI/SNF complex. EPZ-6438 (tazemetostat) is a selective small molecule inhibitor of the histone methyltransferase EZH2.¹ Tazemetostat will be administered orally twice daily at the recommended phase 2 dose (RP2D) as determined by the ongoing pediatric phase 1 trial. The primary endpoint will be objective response rate as determined by RECIST. Progression-free survival (PFS) will be assessed as a secondary endpoint.

EXPERIMENTAL DESIGN SCHEMA

For patient(s) enrolled Pre-amendment #3B:

Day 1-28	Day 28
Tazemetostat 1200 mg/m ² /dose (Orally, twice daily)	Evaluation

For patient(s) enrolled post-amendment #3B:

	Day 1-28	Day 28
Patients without CNS involvement	Tazemetostat 520mg/m ² /dose (Orally, twice daily)	Evaluation
Patients with CNS involvement	Tazemetostat 1200 mg/m ² /dose (Orally, twice daily)	Evaluation

Tazemetostat will be administered orally twice daily (based on disease location per above table); a cycle will be 28 days.

Tumor evaluations will occur at the end of every other cycle x 3, then every 3 cycles.

Therapy will be discontinued if there is evidence of progressive disease or drug related dose-limiting toxicity that requires removal from therapy ([Section 6.0](#)). Therapy may otherwise continue for up to 2 years (maximum of 26 cycles) provided the patient meets the criteria for starting subsequent cycles ([Section 5.2](#)) and does not meet any of the criteria for removal from protocol therapy criteria ([Section 10.0](#)).

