5.0 TREATMENT PROGRAM

5.1 Overview of Treatment Plan

For patient(s) enrolled pre-amendment #3B:

Day 1-28	Day 28
Tazemetostat 1200 mg/m²/dose (Orally, twice daily)	Evaluation

For patient(s) enrolled post-amendment #3B:

	Day 1-28	Day 28
Patients without CNS involvement	Tazemetostat 520mg/m²/dose (Orally, twice daily)	Evaluation
Patients with CNS involvement	Tazemetostat 1200 mg/m²/dose (Orally, twice daily)	Evaluation

Tazemetostat will be administered as a liquid suspension at a dose of 520 mg/m²/dose orally, twice daily (for patients without any CNS involvement); or 1200 mg/m²/dose orally twice daily (for patients with CNS involvement) (based on disease location per above table); without regard to meals with no less than 8 hours between each dose. For patient(s) enrolled pre-amendment #3B Tazemetostat will be administered orally at the MTD and recommended phase 2 dose (RP2D) of 1200 mg/m²/dose BID. If vomiting occurs after taking oral suspension formulation, the dose should NOT be repeated and the next dose should be administered at the regularly scheduled time. See [Section 9.1.6](#) and [Appendix](#)

[IV](#) for additional oral suspension administration and preparation instructions. See [Appendix V](#) for treatment roadmap.

Therapy will be discontinued if there is evidence of progressive disease or drug related dose-limiting toxicity that requires removal from therapy ([Section 6.0](#)). Therapy may otherwise continue for up to 2 years provided the patient meets the criteria for starting subsequent cycles ([Section 5.2](#)) and does not meet any of the criteria for removal from protocol therapy criteria ([Section 10.0](#)).

A cycle of therapy is considered to be 28 days. A cycle may be repeated up to a total duration of therapy of 2 years (maximum 26 cycles).

All patients with CNS involvement enrolled after AMD#3 will be treated at the established pediatric MTD/RP2D which is 1200 mg/m²/dose BID. All patients without any CNS involvement patients enrolled after AMD#3 will be treated at the lower starting dose of 520mg/m²/dose BID. (See [Section 6.1](#) and [Section 6.2](#)).

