8.0 EVALUATIONS/MATERIAL AND DATA TO BE ACCESSIONED

8.1 Required Clinical, Laboratory and Disease Evaluation

All clinical and laboratory studies to determine eligibility must be performed within 7 days prior to enrollment unless otherwise indicated. Laboratory values used to assess eligibility (see [Section 4.0](#)) must be no older than seven (7) days at the start of therapy. Laboratory tests need **not** be repeated if therapy starts **within** seven (7) days of obtaining labs to assess eligibility. If a post-enrollment lab value is outside the limits of eligibility, or laboratory values are older than 7 days, then the following laboratory evaluations must be re-checked within 48 hours prior to initiating therapy: CBC with differential, bilirubin, ALT (SGPT) and serum creatinine. If the recheck is outside the limits of eligibility, the patient may not receive protocol therapy and will be considered off protocol therapy. Imaging studies, bone marrow aspirate and/or biopsy, must be obtained within 14 days prior to start of protocol therapy (repeat the tumor imaging if necessary).

STUDIES TO BE OBTAINED	Pre-Study	During Cycle 1	Prior to Subsequent Cycles [^]
History	X	Weekly	X
Physical Exam with vital signs	X	Weekly	X
Neurologic Exam	X		X
Height, weight, BSA	X		X
Performance Status	X		
Pregnancy Test ¹	X		
CBC, differential ¹⁰ , platelets	X	Weekly ^{2,3}	X ^{2,3}
Urinalysis	X		
Electrolytes including Ca ⁺⁺ , PO ₄ , Mg ⁺⁺	X	Weekly	X
Creatinine, ALT, bilirubin	X	Weekly	X
Albumin	X		X
Bromide Level	X		X
INR	X		
EKG	X		Every 3 cycles
Tumor Disease Evaluation ^{4-A, 4-B, 4-C}	X		Every other cycle x 3 then q 3 cycles ⁴
Bone Marrow Aspirate and/or biopsy ^{5,6}	X		
Plain radiograph tibial growth plate (Bone X-Ray Tests) ⁹	X		Prior to cycles 2, 5 and every 6 months
Patient Diary ⁷		Weekly	X
Circulating Tumor DNA (ctDNA-optional) ⁸			Cycle 5, Day 1 and (for patients receiving ≥ 5 cycles only) at end of Protocol Therapy OR disease progression

[^] Studies may be obtained within 72 hours prior to the start of the subsequent cycle.

¹ Women of childbearing potential require a negative pregnancy test prior to starting treatment; sexually

- active patients must use an acceptable method of birth control. Abstinence is an acceptable method of birth control.
- 2 If patients have Grade 4 neutropenia then CBCs should be checked at least every other day until recovery to Grade 3.

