Any eligible patient who is enrolled and receives at least one dose of protocol therapy will be considered evaluable for response. Any patient who receives non-protocol anti-cancer therapy during the response evaluation period will be considered a non-responder for the purposes of the statistical rule, unless they show an objective response prior to receiving the non-protocol anti-cancer therapy (in which case they will be considered a responder). Patients who demonstrate a complete or partial response confirmed by central review will be considered to have experienced a response. When opening expansion cohorts, the evaluation period for determination of best response will be 6 treatment cycles. All other patients will be considered non-responders. Patients who are not evaluable for response evaluation may be replaced for the purposes of the statistical rule. All patients considered to have a response (CR or PR) must have imaging studies reviewed centrally at the COG. Centers will be notified by the COG about requests for scans of patients with stable disease. Preliminary assessment of activity using institutionally provided tumor measurements will be entered into CDUS quarterly. The central review by COG will be provided as the final reviewed assessment of response when such becomes available.

11.6 **Evaluability for Toxicity**

All eligible patients who receive at least one dose of protocol therapy will be considered in the evaluation of toxicity.

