12.3 Response Criteria for Patients with Solid Tumors

See the table in [Section 8.0](#) for the schedule of tumor evaluations. Eligible patients must have measurable disease present at baseline and have had their disease re-evaluated after one dose of protocol therapy. In addition to the scheduled scans, a confirmatory scan should be obtained on the next consecutive cycle following initial documentation of objective response.

As outlined, patients will be assigned to one of the following categories for assessment of response: a) solid tumor (non-CNS) and measurable disease ([Section 12.4](#)); b) neuroblastoma with MIBG positive lesions ([Section 12.5](#)); c) CNS tumor ([Section 12.7](#)); and d) non-Hodgkin lymphoma/histiocytosis ([Section 12.8](#)). Note: Neuroblastoma patients who do not have MIBG positive lesions should be assessed for response as solid tumor patients with measurable disease.

Response and progression will be evaluated in this study using the revised Response Evaluation Criteria in Solid Tumors (RECIST) guideline (version 1.1) [*Eur J Ca* 45:228-247, 2009]. Key points are that 5 target lesions are identified and that changes in the *largest* diameter (unidimensional measurement) of the tumor lesions but the *shortest* diameter of malignant lymph nodes are used in the RECIST v 1.1 criteria.

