12.4.3 Overall Response Assessment

Table 1: For Patients with Measurable Disease (i.e., Target Disease)

Target Lesions	Non-Target Lesions	New Lesions	Overall Response	Best Overall Response when Confirmation is Required*
CR	CR	No	CR	≥ 28 days Confirmation
CR	Non-CR/Non-PD	No	PR	≥ 28 days Confirmation
CR	Not evaluated	No	PR	
PR	Non-CR/Non-PD/not evaluated	No	PR	
SD	Non-	No	SD	documented at least once ≥

	CR/Non-PD/not evaluated			28 days from baseline
PD	Any	Yes or No	PD	no prior SD, PR or CR
Any	PD**	Yes or No	PD	
Any	Any	Yes	PD	
* See RECIST 1.1 manuscript for further details on what is evidence of a new lesion.				
** In exceptional circumstances, unequivocal progression in non-target lesions may be accepted as disease progression.				
Note: Patients with a global deterioration of health status requiring discontinuation of treatment without objective evidence of disease progression at that time should be reported as “ symptomatic deterioration. ” Every effort should be made to document the objective progression even after discontinuation of treatment.				

Table 2: For Patients with Non-Measurable Disease (i.e., Non-Target Disease)

Non-Target Lesions	New Lesions	Overall Response
CR	No	CR
Non-CR/non-PD	No	Non-CR/non-PD*
Not all evaluated	No	not evaluated
Unequivocal PD	Yes or No	PD
Any	Yes	PD

* ‘Non-CR/non-PD’ is preferred over ‘stable disease’ for non-target disease since SD is increasingly used as an endpoint for assessment of efficacy in some trials so to assign this category when no lesions can be measured is not advised
		

Table 3: Overall Response for Patients with Neuroblastoma and Measurable Disease

CT/MRI	MIBG	Bone Scan	Bone Marrow	Catechol	Overall
PD	Any	Any	Any	Any	PD
Any	PD	Any	Any	Any	PD
Any	Any	PD	Any	Any	PD
Any	Any	Any	PD	Any	PD
SD	CR/PR/SD	Non-PD	Non-PD	Any	SD
PR	CR/PR	Non-PD	Non-PD	Any	PR
CR/PR	PR	Non-PD	Non-PD	Any	PR
CR	CR	Non-PD	Non-PD	Elevated	PR
CR	CR	CR	CR	Normal	CR

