12.9.1 Evaluation of Best Overall Response

The best overall response is the best response recorded from the start of the treatment until disease progression/recurrence (taking as reference for progressive disease the smallest measurements recorded since the treatment started). The patient's best response assignment will depend on the achievement of both measurement and confirmation criteria.

Table 5. Sequences of overall response assessments with corresponding best response.

1 st Assessment	2 nd Assessment	Best Response
Progression		Progressive disease
Stable, PR, CR	Progression	Progressive disease
Stable	Stable	Stable
Stable	PR, CR	Stable
Stable	Not done	Not RECIST classifiable
PR	PR	PR
PR	CR	PR
PR, CR	Not done	Not RECIST classifiable
CR	CR	CR

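### Two minimum intervals for confirming a response (3 weeks in Section 12.9, 28 days in Table 1) cover the same solid-tumour patients, and Table 5 has no row for a response that begins after the first assessment

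*Combined protocol and SAP*

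**What the plan says.** - **Section 12.9, all disease types.** Best response needs two objective status determinations, "obtained on two consecutive determinations, separated by at least a 3 week time period, are required". A best response of PR takes two determinations of PR or better before progression.
- **Section 12.4.3, Table 1, measurable solid tumours.** The column for best overall response when confirmation is required carries "≥ 28 days Confirmation". In the text available for this review that entry is legible on the two rows where the target lesions are in CR. The cell on the target-PR row is blank, possibly a merged cell lost in extraction.
- **Section 12.4.4.** Best response for these patients is to be determined as Section 12.9 sets out.
- **Scan timing.** The Experimental Design Schema states "Tumor evaluations will occur at the end of every other cycle x 3, then every 3 cycles". Section 12.3 adds that "a confirmatory scan should be obtained on the next consecutive cycle following initial documentation of objective response". Section 5.1 fixes the cycle: "A cycle of therapy is considered to be 28 days". The schedule footnote in Section 8.1 allows slack: "Studies may be obtained within 72 hours prior to the start of the subsequent cycle".
- **Section 12.9.1, Table 5.** Titled "Sequences of overall response assessments with corresponding best response", it has columns for a first and a second assessment only. Stable followed by PR or CR is assigned Stable. The text above the table runs best response from the start of treatment to progression or recurrence.
- **Section 11.5.** "When opening expansion cohorts, the evaluation period for determination of best response will be 6 treatment cycles".
- **Sections 11.3.1 and 11.4.** The match is a success with at least 3 responders in 20, a responder being a patient whose best response on study is PR or CR.

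**The concern.** Section 12.9.1 makes best response depend on confirmation as well as measurement, so the confirmation interval is part of the primary endpoint. Two different minimum intervals apply to one group of patients, and the planned scan timing straddles the longer one. The same patient can therefore be a responder under one section and a non-responder under another, with no deviation from the schedule.

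Table 5 leaves a second gap. A response that first appears at the second scheduled scan and is confirmed at the next is an ordinary course under this schedule, yet no row describes it.

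The verdict is a count against a threshold of 3, so one patient can settle it. If the choice between the rules is made after the scans have been read, the decision rule is no longer fully pre-specified.

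**Working it through.** **Inputs.** N = 20, success at 3 or more responders, null rate 5%, target rate 25%, stated alpha 10% and power 90% (Sections 11.3 and 11.3.1); 28-day cycle (5.1); confirmatory scan on the next cycle (12.3 and footnote 4 of 8.1); 72-hour window (8.1); minimum intervals of 21 days (12.9) and 28 days (Table 1).

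**Step 1: reproduce the design.** P(X ≥ 3) = 1 − P(0) − P(1) − P(2), X binomial with n = 20.
- At 25%: 1 − 0.0032 − 0.0211 − 0.0669 = 0.909, so power is 90.9%.
- At 5%: 1 − 0.3585 − 0.3774 − 0.1887 = 0.0755, so exact alpha is 7.5%, below the 10% ceiling.

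Both agree with the plan.

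**Step 2: on-schedule interval.** Let a be the days by which the first scan is early and b the days by which the confirmatory scan is early, each from 0 to 3. Interval = 28 + a − b, which runs from 25 to 31 days.

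| Interval (days) | Section 12.9 (≥ 21) | Table 1 (≥ 28) |
|---|---|---|
| 25 to 27 | confirmed | not confirmed |
| 28 to 31 | confirmed | confirmed |

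If a and b are independent and equally likely to be 0, 1, 2 or 3 (an assumption; the documents give no distribution), 6 of the 16 combinations are below 28 days, or 37.5% of on-schedule confirmations. Delayed cycles would lower that share.

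**Step 3: Table 5 against the 12.9 text.**

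| Sequence | 12.9 text | Table 5 |
|---|---|---|
| Stable, PR, nothing further | Stable (only one PR determination) | Stable |
| Stable (cycle 2), PR (cycle 4), PR (cycle 5) | PR | Stable on the first two assessments; no row for the third |

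The first line agrees. The difficulty is confined to the second.

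**Step 4: six-cycle window.** Six cycles are 6 × 28 = 168 days. A response first seen at the cycle-6 scan (about day 168) is due for confirmation at the end of cycle 7, between day 193 and day 196. Even a first scan 3 days early with a 21-day confirmation gives 168 − 3 + 21 = day 186. Confirmation always falls after the window closes.

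**Step 5: effect on the primary decision.**
- P(X = 3) at 25% is 0.134. In that case losing one responder turns success into failure.
- If a share q of true responders lost that status, power is P(X ≥ 3) at 0.25 × (1 − q).

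| q (assumed) | Effective rate | Power |
|---|---|---|
| 0 | 25.0% | 90.9% |
| 10% | 22.5% | 86.1% |
| 20% | 20.0% | 79.4% |
| 37.5% | 15.6% | 62.5% |

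The last row is a bound and not an estimate, for the reasons given under the objection.

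**The case against.** The best defence is that the plan already names the governing rule: Section 12.4.4 points Table 1 patients to 12.9. Both intervals are also minimums, so any scan at 28 days or later meets both. This stands in part. It is a good reason to resolve the conflict in favour of 12.9. It does not remove the conflict, because the Table 1 column is itself about confirmed best overall response and nothing sets it aside.

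The reach is limited, and that stands in full. CNS tumours (12.7), lymphoma and histiocytosis (12.8) and neuroblastoma with MIBG-positive disease only (12.5) have only the 3-week rule. Within Table 1, whether the 28-day entry extends to the target-PR row cannot be settled from the extracted table.

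A reader might infer three stronger things that the documents do not support.

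- *That power could fall to 62.5%.* This applies the 37.5% share to every responder, including those outside Table 1, and supposes no later scan. Footnote 4 in Section 8.1 lets scans restart two cycles after the confirmatory one, so a continuing response can still be confirmed beyond 28 days. If half of responders fall under Table 1 and half of the short-interval cases have no later scan (both assumptions), the loss is 0.375 × 0.5 × 0.5 = 9.4% and power is 86.4%.
- *That the Stable-then-PR row of Table 5 contradicts 12.9.* With only two assessments the two agree, since the response is unconfirmed. The defect is a missing sequence.
- *That the six-cycle window removes late responders from the 3-of-20 count.* Section 11.5 ties the window to opening expansion cohorts. The primary definition in 11.4 has no cycle limit, so a cycle-6 response confirmed at cycle 7 counts toward the primary decision.

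**Conclusion.** The concern holds in a limited form. For non-CNS solid tumours with measurable disease, two stated confirmation intervals conflict, and an on-schedule confirmation at 25 to 27 days passes one and fails the other. This is certain for the target-CR rows of Table 1 and unclear for the target-PR row. Table 5 is incomplete for responses that begin at the second assessment or later; this reaches every disease group, because each is classified by best response.

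The size cannot be fixed from the documents. What follows exactly from the design is the 13.4% chance, at a true rate of 25%, that the count lands on 3 and losing a single responder decides the trial. That is the chance that the result is fragile, not the chance that a patient is reclassified. The power figures of 86.1% and 79.4% rest on assumed losses of 10% and 20%.

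The sample size, threshold, alpha and power are correct as stated. The six-cycle question is a minor gap in the expansion trigger only.

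**What to change.** 1. **Table 1.** Replace the 28-day entry with the 12.9 interval: confirmed at the next-cycle scan, at least 3 weeks after first documentation. State which rows it covers, including the target-PR row.
2. **Table 5.** Keep the Stable-then-PR/CR row, which is right for an unconfirmed response; replacing it would delete a correct result. Add a row or note that a PR or CR first seen at a later assessment, and confirmed by the next consecutive assessment before progression, is a best response of PR or CR.
3. **Section 11.5 (minor, expansion trigger only).** State whether a response first documented at the cycle-6 scan and confirmed at cycle 7 counts toward opening an expansion cohort.

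The cost is edits to two tables and one sentence, with no new scans or patients and no change to the design figures. If item 3 is answered yes, an expansion decision may wait one cycle for a confirmatory scan that is already scheduled. The edits should be in place before responses are adjudicated.

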12.9.1 Evaluation of Best Overall Response

The best overall response is the best response recorded from the start of the treatment until disease progression/recurrence (taking as reference for progressive disease the smallest measurements recorded since the treatment started). The patient's best response assignment will depend on the achievement of both measurement and confirmation criteria.

Table 5. Sequences of overall response assessments with corresponding best response.

1 st Assessment	2 nd Assessment	Best Response
Progression		Progressive disease
Stable, PR, CR	Progression	Progressive disease
Stable	Stable	Stable
Stable	PR, CR	Stable
Stable	Not done	Not RECIST classifiable
PR	PR	PR
PR	CR	PR
PR, CR	Not done	Not RECIST classifiable
CR	CR	CR

12.9.2 Duration of Response

Duration of overall response: The duration of overall response is measured from the time measurement criteria are met for CR or PR (whichever is first recorded) until the first date that recurrent or progressive disease is objectively documented (taking as reference for progressive disease the smallest measurements recorded since the treatment started).

The duration of overall CR is measured from the time measurement criteria are first met for CR until the first date that progressive disease is objectively documented.

Duration of stable disease: Stable disease is measured from the start of the treatment until the criteria for progression are met, taking as reference the smallest measurements recorded since the treatment started, including the baseline measurements.

